1.10 Study Arm Assignment, Randomization, and Subject Retention

Participants will be assigned to either intervention, both interventions, or no intervention arms after the run-in period in a random manner until 40 participants are enrolled into each arm. Permuted block randomization stratified by WHO functional class (I/II vs. III) will be used to ensure approximate balance of treatment groups within each stratum over time. Based on our previous studies in PAH subjects in our catchment area, African Americans will represent approximately 16% of the study population. Randomization will be performed in small blocks, which vary in size. Investigators will be unaware of the size or order of the blocks. Projected dropout during the 12 week study has been incorporated into the power calculations. The Data Safety Monitor Board may be unblinded at any time to investigate possible adverse events. Procedures for reporting adverse events are outlined in section 7.0.

The group randomization code will be maintained by the research coordinator. The code is to be broken only if knowledge of group assignment for that subject is required to initiate appropriate therapy of an adverse event (AE) or if the safety of the subject is at serious risk without knowledge of the group assignment. The decision to unmask will be made by the PI and/or Co-PI. The Data Safety Monitoring Board will be notified as soon as possible.

Study Designs

1.11 Overview

We propose a phase II, 2x2 factorial randomized, blinded trial testing metformin versus placebo and an mHealth intervention (mHealth) versus usual care of 12 weeks.

1.12 Monitoring Device

The Fitbit Charge HR tri-axial accelerometer will be used to continuously gather data on physical activity, heart rate, and sleep. This device provides feedback in units of activity (steps, stairs climbed, activity time, and exercise time) and heart rate (per second when active, per 5 seconds when inactive). It has been validated against research devices in free-living conditions and is relatively inexpensive.

1.13 Fitbit Application and Data Management

During enrollment, study personnel will install the Fitbit on the subject's smartphone, paired via Bluetooth 4.0 to the Fitbit Charge HR. The Fitabase subscription service (<https://www.fitabase.com/>) will be used to create a study dashboard, enabling real-time monitoring of battery charge, device syncing, and physical activity variables allowing real-time monitoring of participant compliance with the study protocol. Fitabase is a HIPPA compliant platform that can link and aggregate the Application Programming Interfaces of the Fitbit Charge HR. Real time activity data will be transmitted from the subject's smartphone to our mHealth platform via cellular network. The Charge HR has a battery life of 5 days and recharges in 1-2 hours. Subjects will be instructed to leave the app running and Bluetooth enabled for the duration of the trial.

1.14 mHealth Intervention

Our HIPPA compliant texting platform is linked to the Fitbit Application Program Interface. Real time activity data will be transmitted from the subject's smartphone to our mHealth platform via cellular network. Subjects assigned to the texting arm will receive 3 texts/day in sync with their preferred morning, lunch, and evening leisure schedule, which is defined at enrollment. These texts will use personal, disease-specific, and provider information (**Table 1**) to deliver 2 types of messages customized to the current step count and sent in equal proportion. Messages are designed to facilitate self-awareness, reinforce step targets, and link physical activity with a reward or memorable cue.

Booster:

“Megan, you were pretty active yesterday! You got 8994 steps, which is close to your goal of 10,000. There are immediate benefits to exercise: you will feel better and have more energy!”

Positive reinforcement:

“Jon, you are on track to have a VERY ACTIVE day! Already halfway to your target of 10,000 steps – Outstanding

Subjects in both study arms may receive additional texts during the day for reminders about charging,

Table 1. Factors in Personalization of Text Messages

Preferred name	Occupation
Age	Name of spouse/partner
Sex	Name of children
Physician name	Name of dog
Preferred activity	Local park
Favorite athlete	Gym
Body mass index	Work schedule
Other co-morbidities	Television watching habits
PAH-specific medications	

syncing, and the Fitbit Charge HR. Subjects will receive weekly email reminders about the importance of wearing their device from a secure email address created for this study. Subjects can email this account with study questions. If there is loss of data transmission for a full day, subjects will be emailed with a reminder to wear their device and/or reestablish a connection with their phone. After 3 days of absent data, another email reminder will be sent and the study coordinator will call the subject to determine the cause. If subjects have regularly scheduled clinic visits with their treating physician, they will be counseled not to reveal their group assignment.

1.15 Run-in Period and Step Count Targets

We will use a two-week run-in period, which will improve our ability to identify a true baseline step count and reduce dropout after randomization. Participants will wear the Fitbit Charge HR device 24 hours a day for seven days a week (excluding only bathing or showering) to determine their baseline daily step count. We will assume a Hawthorne or observer effect during the first week of the run-in period and discard this data. The baseline daily step count will be calculated as total steps during run-in Week 2 divided by 7 days. Randomization will occur after the run-in phase to account for potential dropout during this period. Participants displaying noncompliance during the run-in period will not be randomized. Noncompliance will be defined as having more than one bad data or no data day per week. However, depending on the reason for noncompliance, this requirement may be waived at the discretion of the PI and study team.

The initial daily step target Weeks 1-4 for the intervention group will be 20% higher than the run-in baseline value. For example, if the run-in daily step count is 2,000 steps/day, the daily step target for Weeks 1-4 will be 2,400 steps/day. An increment of 20% was selected because it reflects the average increase in treadmill workload achieved over 4 weeks in chronic obstructive lung disease patients with PH who attend pulmonary rehabilitation at our facility. Average daily step counts during Week 4 will be calculated and used to define the target (20% above the Week 4 average) for Weeks 5-8. The daily target for Weeks 9-12 will be calculated in the same manner. New targets will be communicated with patients via text message. If outliers are observed, we reserve the right to adjust the increase in the daily step target. Outliers will be identified based on preset qualifications for days providing good data.

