1.25 Missing Data and Dropouts

For all endpoints, the primary analysis will be intention-to-treat (ITT): all subjects randomized with a post-intervention endpoint measurement will be included. For endpoints based on measurements collected at the end of the study, individuals who do not complete follow-up cannot be included in analyses of those endpoints. Subjects who stop study interventions at any point of the study but agree to come back for the final data collection will be invited to do so to facilitate the ITT analysis. A per-protocol analysis will be conducted as a secondary analysis for the primary endpoints. Any subject who is identified as a major protocol violator will not be included. Major protocol violators will be defined as subjects randomized but non-compliant with wearing the accelerometer (i.e. missing $\geq 1/2$ of total days) and others

identified by a committee not related to the study (XXX usually the study team determines a list of protocol violators before data un-blinding, but this is a single blinded study and that [name] and [name] know who gets what and the endpoints, that complicates it a bit) .

Subjects who drop out will be replaced up to a total of 35 per group. Built-in alerts will be triggered if there is a prolonged lapse in data transmission in real-time activity tracking. Protocols to email, then call subjects will be followed to determine the cause of missing data and find a solution. The Fitbit device will store data for 28 days so even if data is not being transmitted, it will not be lost. A stock of new devices will be kept on hand to overnight ship to subjects if the Fitbit device fails to capture data or stops working.

In the event of missing data, we will conservatively impute missing data to perform analyses with and without imputed missing data to corroborate findings.

Conservative imputation strategies could include assuming worst case scenario for subjects on the intervention, best case for subjects on the control, or assuming the observed mean of the control group for the subjects on the intervention. A multiple imputation procedure implemented in the aregImpute function in the Hmisc package in R (R Package; Version 3.0-10) will be used. The analysis with imputation will serve primarily as a sensitivity analysis. The potential drop-out is considered in the power calculation to minimize its impact.

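### The run-in step baseline divides by a fixed 7 days although one bad or no-data day is allowed; one typical no-data day cuts the Weeks 1-4 step increase from 20% to about 3%.

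*Combined protocol and SAP*

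**What the plan says.** Section 1.15 discards the first run-in week and takes the baseline from the second: "The baseline daily step count will be calculated as total steps during run-in Week 2 divided by 7 days". The target for the first four treatment weeks follows from it: "The initial daily step target Weeks 1-4 for the intervention group will be 20% higher than the run-in baseline value". The worked example in that section goes from 2,000 to 2,400 steps/day.

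The same section defines who may be randomized: "Noncompliance will be defined as having more than one bad data or no data day per week". One such day is therefore acceptable. Beyond that, "this requirement may be waived at the discretion of the PI and study team". Section 1.19.2 repeats both the definition and the waiver.

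Later targets are reset from achieved steps: "Average daily step counts during Week 4 will be calculated and used to define the target" for Weeks 5-8, and in the same way for Weeks 9-12. No divisor is given for these averages.

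Three provisions bear on missing or odd data:

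- Section 1.15: "If outliers are observed, we reserve the right to adjust the increase in the daily step target". It refers to preset qualifications for good-data days but does not list them.
- Section 1.14: "If there is loss of data transmission for a full day, subjects will be emailed with a reminder to wear their device".
- Section 1.25: "The Fitbit device will store data for 28 days so even if data is not being transmitted, it will not be lost".

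The Protocol Summary lists the frequency of daily goal attainment as a secondary endpoint, compared between groups with and without mHealth. Section 1.15 sets targets for the intervention group only.

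**The concern.** A divisor of 7 is right only when all seven days were recorded. The plan accepts six, and by waiver fewer. With the divisor fixed and no imputation, each lost day enters as zero steps and the baseline falls. The error runs in one direction, because uncaptured steps can only lower the total.

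The six-day case is foreseeable. Section 1.22.13 counts weeks with at least six days of activity data as a fidelity measure. Section 1.13 gives a battery life of 5 days, and section 1.25 keeps spare devices for failures.

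What is at stake is the content of the activity intervention. The run-in is meant to find a true baseline, and under section 1.14 the texts reinforce the step target. An affected mHealth subject would be prompted for about four weeks towards a goal close to current activity. The same ambiguity can recur in the averages that reset the targets and in the week-12 average daily step count.

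A secondary point concerns goal attainment. It has no defined goal in the two arms without mHealth, so the listed comparison with those arms cannot be made as written.

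**Working it through.** **Inputs.** All are from section 1.15: divisor 7; one bad or no-data day allowed in the week, more by waiver; increment 20%; worked example 2,000 steps/day.

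**The plan's own figure.** Seven good days at 2,000: 14,000/7 = 2,000, and 1.2 × 2,000 = 2,400. This reproduces.

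**One no-data day of typical activity.**

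- Recorded total: 6 × 2,000 = 12,000
- Baseline: 12,000/7 = 1,714, which is 1/7 (14.3%) too low
- Target: 1.2 × 12,000/7 = 2,057
- Target relative to true activity: 1.2 × 6/7 = 1.029, or +2.9%
- Shortfall: 2,400 − 2,057 = 343; increase delivered: 57 of 400 steps (14.3%)

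The ratio 1.2 × 6/7 does not depend on the step level.

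**A partly captured day.** If a share c of a typical day's steps is captured, target/true = 1.2 × (6 + c)/7.

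| c | target/true | target at 2,000 |
|---|---|---|
| 0 | 1.029 | 2,057 |
| 0.5 | 1.114 | 2,229 |
| 1 | 1.200 | 2,400 |

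**A lost day that was not typical.** The documents give no day-to-day variation, so I assume that the lost day had r times the mean of the other six days, with r from 0.75 to 1.25. In units of that mean, the true 7-day mean is (6 + r)/7 and the fixed-divisor baseline is 6/7. Hence:

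- understatement of the baseline = r/(6 + r)
- target/true with divisor 7 = 7.2/(6 + r)
- target/true with divisor 6 = 8.4/(6 + r)

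| r | baseline too low by | divisor 7 | divisor 6 (valid days) |
|---|---|---|---|
| 0.75 | 11.1% | +6.7% | +24.4% |
| 1 | 14.3% | +2.9% | +20.0% |
| 1.25 | 17.2% | −0.7% | +15.9% |

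The valid-day divisor gives the intended 20% when the lost day is typical, and scatters on both sides of it otherwise. The fixed divisor falls well short in every row.

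**Two no-data days under a waiver.** 1.2 × 5/7 = 0.857. At 2,000 steps/day the target is 1,714, which is 14.3% below true activity.

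**Duration.** Weeks 1-4 are 28 of 84 treatment days (12 weeks × 7).

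**Do other provisions repair this?** The outlier clause reserves a right and requires nothing; it concerns the size of the increase and leaves the baseline as computed. The reminder is sent after a full day without transmission. Device storage recovers steps that were recorded but not sent. It cannot recover a day on which the device was not worn or failed to record.

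**The case against.** The strongest reply is that this is an unwritten missing-day rule with a small consequence. The plan's only worked figure is correct, and a divisor of 7 suits the round-the-clock wear that section 1.15 asks for. The figure of about 3% needs a whole Week 2 day with no recoverable steps. A bad day in the first run-in week changes nothing, because that week is discarded. Real-time monitoring, reminders, 28-day storage and replacement devices should make such days uncommon, and staff could use the outlier clause to raise a low target. Targets are reset after Week 4, the covariates named in section 1.24 do not include the run-in step count, and the step endpoint is a comparison at week 12. Dividing by six instead of seven raises an affected subject's target by one sixth (7/6), which might be read as altering the intensity of the intervention. Enrolment may also be far advanced: version 1.0 dates from January 2018, the latest ethics approval from April 2024, and enrolment was planned over 4.5 years.

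Much of this stands as a limit on size. The 3% is for a fully lost, typical day; the frequency is unknown; no effect on the primary endpoint or on a named analysis is shown; and a late change would help few subjects. It does not remove the conflict. The divisor is stated, the six-day week is expressly permitted, and the two together give a wrong baseline. The safeguards leave non-wear and device failure uncovered, and the outlier clause is optional. The higher target under a valid-day divisor is the increase that the plan itself specifies, applied to a correctly measured baseline.

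**Conclusion.** The concern holds. For a mHealth subject with one fully lost Week 2 day of typical activity, the Weeks 1-4 target is 2.9% above true activity where the plan intends 20%. Under the assumed range of 0.75 to 1.25 for the lost day, the figure lies between +6.7% and −0.7%. A partly captured typical day gives between +2.9% and +20%, and two lost days under a waiver give −14.3%.

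These figures rest on the literal reading that an unrecorded day adds no steps to the total. Subjects with seven good days are unaffected. The documents do not show how many subjects are affected, or how far a lower target changes actual activity. The plan should be corrected, but the validity of the primary comparison does not depend on it.

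The secondary point also holds: goal attainment can be compared between the two mHealth arms but has no defined goal in the other two.

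**What to change.** Reconcile the divisor in section 1.15 with the missing-day allowance. Compute the baseline as total steps on valid Week 2 days divided by the number of valid days, using the plan's own good-data-day qualifications, and write those qualifications into the protocol. State the same rule for the averages that reset the later targets and for the week-12 average daily step count. The 20% increment and the symptom-based goal reductions in section 1.42 stay as they are.

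For goal attainment, either restrict the endpoint to the two mHealth arms or define one reference that is computed alike for every subject.

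The cost of the baseline change is one sentence and one change in the target algorithm, with no new data collected. The documents do not state enrolment status. If subjects have already been treated, record the date of the change and, where it matters, report step analyses before and after it. Earlier run-in baselines can be recomputed if the daily counts were kept, but targets already issued cannot be changed.

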- Composite endpoint of 10% or greater improvement in six minute walk distance over baseline or improvement of at least one WHO functional class at week 12.

SECONDARY ENDPOINTS:

- Difference in body weight between mHealth intervention or no intervention and/or metformin or placebo groups at week 12.
- Difference in BMI between mHealth intervention or no intervention and/or metformin or placebo groups at week 12.
- Difference in absolute 6MWD between mHealth intervention or no intervention and/or metformin or placebo groups at week 12.
- Difference in Borg Dyspnea Score between mHealth intervention or no intervention and/or metformin or placebo groups at week 12.
- Difference in emPHasis-10 quality of life survey score between mHealth intervention or no intervention and/or metformin or placebo groups at week 12.
- Difference in WHO functional classification between mHealth intervention or no intervention and/or metformin or placebo groups at week 12.
- Difference in average daily step count between mHealth intervention or no intervention and/or metformin or placebo groups at week 12.
- Difference in frequency of daily goal attainment between mHealth intervention or no intervention and/or metformin or placebo groups at week 12.
- Difference in daily goal aerobic time between mHealth intervention or no intervention and/or metformin or placebo groups at week 12.

- Difference in total daily activity between mHealth intervention and/or metformin and no intervention and/or metformin or placebo groups at week 12.
- Difference in resting heart rate between mHealth intervention or no intervention and/or metformin or placebo groups at week 12.
- Difference in HOMA-IR between mHealth intervention or no intervention and/or metformin or placebo groups at week 12.
- Difference in urine and plasma estradiol between mHealth intervention or no intervention and/or metformin or placebo groups at week 12.
- Difference in urine and plasma estrogen metabolites between mHealth intervention or no intervention and/or metformin or placebo groups at week 12.
- Difference in plasma lipid profiles between mHealth intervention or no intervention and/or metformin or placebo groups at week 12.
- Difference in plasma free fatty acid profiles between mHealth intervention or no intervention and/or metformin or placebo groups at week 12.
- Difference in plasma acylcarnitine profiles between mHealth intervention or no intervention and/or metformin or placebo groups at week 12.

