1.21 Assessments of Efficacy

Primary Endpoint: Composite endpoint of 10% or greater improvement in six minute walk distance over baseline or improvement of at least one WHO functional class at week 12.

Secondary Endpoints: There are several secondary objectives of this study. They include:

- To assess the effect of a mHealth intervention or no intervention and/or metformin or placebo on body weight at week 12.
- To assess the effect of a mHealth intervention or no intervention and/or metformin or placebo on BMI at week 12.
- To assess the effect of a mHealth intervention or no intervention and/or metformin or placebo on absolute 6MWD at week 12.
- To assess the effect of a mHealth intervention or no intervention and/or metformin or placebo on Borg Dyspnea Score at week 12.
- To assess the effect of a mHealth intervention or no intervention and/or metformin or placebo on emPHasis-10 quality of life survey score at week 12.
- To assess the effect of a mHealth intervention or no intervention and/or metformin or placebo on WHO functional classification at week 12.
- To assess the effect of a mHealth intervention or no intervention and/or metformin or placebo on the average daily step count at week 12.
- To assess the effect of a mHealth intervention or no intervention and/or metformin or placebo on frequency of daily goal attainment at week 12.
- To assess the effect of a mHealth intervention or no intervention and/or metformin or placebo on daily aerobic time at week 12.
- To assess the effect of a mHealth intervention or no intervention and/or metformin or placebo on total daily activity at week 12.

- To assess the effect of a mHealth intervention or no intervention and/or metformin or placebo on resting heart rate at week 12.
- To assess the effect of a mHealth intervention or no intervention and/or metformin or placebo on HOMA-IR at week 12.
- To assess the effect of a mHealth intervention or no intervention and/or metformin or placebo on urine and plasma estradiol at week 12.
- To assess the effect of a mHealth intervention or no intervention and/or metformin or placebo on urine and plasma estrogen metabolites at week 12.
- To assess the effect of a mHealth intervention or no intervention and/or metformin or placebo on plasma lipid profiles at week 12.
- To assess the effect of a mHealth intervention or no intervention and/or metformin or placebo on plasma free fatty acid profiles at week 12.

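### Goal attainment is a between-arm endpoint, but usual care has no goal, and the moving mHealth goals make attainment reflect recent change, not the activity level reached

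*Combined protocol and SAP*

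**What the plan says.** The Protocol Summary lists this secondary endpoint: "Difference in frequency of daily goal attainment between mHealth intervention or no intervention and/or metformin or placebo groups at week 12". Secondary aim 8 in section 1.7 and the objectives in section 1.21 ("on frequency of daily goal attainment at week 12") repeat it. All three include subjects who do not receive the mHealth intervention.

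Section 1.15 sets the goals:

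- Weeks 1-4: "The initial daily step target Weeks 1-4 for the intervention group will be 20% higher than the run-in baseline value". Its example: "if the run-in daily step count is 2,000 steps/day, the daily step target for Weeks 1-4 will be 2,400 steps/day".
- Weeks 5-8: the average daily count in week 4 is "used to define the target (20% above the Week 4 average) for Weeks 5-8".
- Weeks 9-12: "The daily target for Weeks 9-12 will be calculated in the same manner". I read this as 20% above the week 8 average.
- Delivery: "New targets will be communicated with patients via text message". Section 1.14 says who gets the activity texts: "Subjects assigned to the texting arm will receive 3 texts/day".

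Targets can also be altered when outliers are seen (1.15) or lowered for symptoms (1.42). Section 1.22.6, which describes the activity measures, names goal attainment but gives no goal for usual care, no denominator and no time window. The same section has subjects wear the tracker throughout, and section 1.15 obtains a run-in baseline before randomization.

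**The concern.** There are two separate problems.

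First, a between-arm difference needs the same quantity in each arm. Usual care makes up two of the four arms, 80 of the 160 planned subjects, and has no goal. An analyst would have to invent one, and that choice could settle the result. If it is made after the data are seen, the definition can follow the result.

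Second, where goals exist they move with the subject's own recent steps. A subject who has raised activity and kept it up is judged against a higher bar, and one who has declined against a lower bar. The reader of a week 12 attainment figure would take it as a measure of activity achieved, and it is not one.

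**Working it through.** **The plan's own figure.** 1.20 x 2,000 = 2,400 steps/day, as section 1.15 states.

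**Which contrasts have a value.** Section 1.24 names three contrasts for the primary endpoint: metformin, exercise, and the combination, each against placebo. If they are carried over to this endpoint, all three use the arm with neither active intervention as reference, and that arm has no goal. Metformin alone against placebo alone has no goal on either side. Any mHealth arm against any usual-care arm has a goal on one side only. That leaves metformin versus placebo within the two mHealth arms.

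**Targets under the moving rule**, with baseline B = 2,000 and each later target = 1.20 x the subject's average in the last week of the preceding block:

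| Subject | Week 4 and week 8 average | Weeks 1-4 | Weeks 5-8 | Weeks 9-12 |
|---|---|---|---|---|
| Up 50% by week 4, then held | 3,000 | 2,400 | 3,600 | 3,600 |
| No change | 2,000 | 2,400 | 2,400 | 2,400 |
| Down 20%, then held | 1,600 | 2,400 | 1,920 | 1,920 |

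**Expected attainment in weeks 9-12.** Take daily steps as normal around the subject's current mean m, with standard deviation CV x m. Then the probability of attaining target T on a day is 1 - Φ((T - m)/(CV x m)). The documents give no day-to-day CV; I assume 0.2 to 0.4, the same for every subject.

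*Moving target, subject flat since week 8.* T = 1.2m, so (T - m)/(CV x m) = 0.2/CV and m cancels:

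- CV 0.2: z = 1.00, 15.9%
- CV 0.3: z = 0.67, 25.2%
- CV 0.4: z = 0.50, 30.9%

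These values apply equally to all three subjects.

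*Fixed threshold, T = 1.2B = 2,400:*

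| Subject | (T - m)/m | CV 0.2 | CV 0.3 | CV 0.4 |
|---|---|---|---|---|
| Up 50% (m = 3,000) | -0.2 | 84.1% | 74.8% | 69.1% |
| No change (m = 2,000) | 0.2 | 15.9% | 25.2% | 30.9% |
| Down 20% (m = 1,600) | 0.5 | 0.6% | 4.8% | 10.6% |

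**What an improvised usual-care goal could do.** Suppose usual care were scored at 1.2 x baseline while mHealth kept its moving targets. An mHealth subject holding a gain of 1,000 steps/day and a usual-care subject with no change would then both score 15.9-30.9%. A sustained gain would show as no difference.

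**The case against.** Several counter-arguments have weight.

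- *The between-arm wording may be template text.* In section 1.7 the same phrasing is attached to fidelity of text transmission, which has no meaning for metformin alone. But the summary objectives and section 1.21 limit fidelity to the mHealth intervention and do not limit goal attainment in this way. This softens the point without removing it.
- *The moving rule is a coherent measure of response to coaching.* It is: it asks whether the latest increment was achieved. A subject who meets every target has goals of 2,400, 2,880 and 3,456, and if averaging 3,456 in week 12 attains the goal on about 50% of days under the symmetric model, more than any flat subject. This supports keeping it as a measure of the intervention, but not as a between-arm measure of activity.
- *A fixed threshold largely dichotomises average daily step count, already an endpoint.* This stands as a cost of the fix. Reporting attainment within the mHealth arms only would be a simpler alternative.

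A reader might also infer three stronger things that the documents do not support:

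- That the endpoint cannot be computed for half the trial. Usual-care subjects have a run-in baseline and wear the tracker, so a notional goal could be computed. It is unspecified, not impossible.
- That the rule penalises improvers, or runs against the treatment effect. The calculation shows insensitivity to the level held, not reversal.
- That at 3,000 steps/day in weeks 9-12 a subject with a 3,456 goal scores 0% and one with a 2,400 goal scores 100%. That needs identical steps every day. With a CV of 0.2-0.4 the figures are about 22-35% and 69-84%. Nor do the cases fit their histories: a subject meeting every target would average about 3,456, and one who never improved would not reach 3,000.

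**Conclusion.** The point holds in two parts. The endpoint has no defined value for any contrast involving usual care; only metformin versus placebo within the mHealth arms follows from the text. Within those arms, attainment reflects recent change, not the level reached.

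The targets follow from the plan's rule, with the weeks 9-12 target read as based on week 8. The percentages rest on normality and on an assumed CV that is the same at every activity level. Under that model the equality of the moving-target rates and the ordering of the fixed-threshold rates hold at every CV shown; the equality would not be exact if the CV changed with activity.

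The consequence is limited to one of about 40 secondary endpoints. The primary endpoint, the sample size and the other activity measures (step count, aerobic time, total daily activity) are unaffected. It should be corrected, but it does not threaten the trial's main conclusion.

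**What to change.** For the between-arm endpoint, define attainment in all four arms as the percentage of week 12 days with good tracker data on which steps are at or above 1.2 x the subject's own run-in baseline. State the rule for a good-data day in advance; section 1.15 refers to preset qualifications but does not give them.

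Report attainment of the texted, moving targets within the mHealth arms only, as a descriptive measure of intervention delivery.

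The cost is one endpoint definition and the good-data-day rule. No new data are needed, and the targets used to deliver the intervention stay unchanged. The price is overlap with average daily step count, so the fixed-threshold result should not be read as independent confirmation of it.
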